6.4 Treatment blinding

This is a blinded study. Participants and investigators will remain blinded to study treatment throughout the study, except where indicated below.

Participants, investigator staff, persons performing the assessments, and the clinical trial team (CTT) will remain blind to the identity of the treatment from the time of randomization until end of study visit applying the following rules:

- Randomization data are kept strictly confidential until the time of unblinding.
- Unblinding will occur in the case of participant emergencies and at the conclusion of the study.
- Unblinding of the CTT members may occur for the purpose of periodic review of the safety data.
- Unblinded results from the planned interim analysis after all participants have completed the Day 29 visit can be shared with the participants and site staff, if deemed appropriate.

The identity of the treatments will be concealed by the use of study drugs that are all identical in packaging, labeling, schedule of administration, appearance, and odor.

Site staff

With the exception of any unblinded site staff identified below, all site staff (including study investigator and study nurse) will be blinded to study treatment throughout the study.

Unblinding a single participant at site for safety reasons (necessary for participant management) will occur via an emergency system in place at the site.

Drug product will be supplied in bulk, so an unblinded pharmacist who is independent of the study team will be required in order to maintain the blind. This unblinded pharmacist at the site will be notified by the IRT system that a participants randomized and to which treatment arm, which will then enable them to prepare the study drug. Appropriate measures must be taken by the unblinded pharmacist to ensure that the treatment assignments are concealed from the rest of the site staff.

Sponsor staff

The following unblinded sponsor roles are required for this study amend as appropriate:

- Unblinded field monitor(s)
- Unblinded clinical staff managing drug re-supply to site
- Unblinded sample analyst(s) CCI

Commercially Confidential Information

The unblinded field monitors are required to review drug accountability and allocation at site. The unblinded monitors are not provided with a randomization list directly but will be unblinded through review of source documentation compiled by the unblinded pharmacist, which details treatment allocation to individual participants.

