10.1.5 Reporting of study treatment errors including misuse/abuse

Medication errors are unintentional errors in the prescribing, dispensing, administration or monitoring of a medicine while under the control of a healthcare professional, participant or consumer (European Medicines Agency (EMA) definition).

Misuse refers to situations where the medicinal product is intentionally and inappropriately used not in accordance with the protocol.

Abuse corresponds to the persistent or sporadic, intentional excessive use of a medicinal product, which is accompanied by harmful physical or psychological effects.

Study treatment errors and uses outside of what is foreseen in the protocol will be recorded on the appropriate CRF irrespective of whether or not associated with an AE/SAE and reported to Safety only if associated with an SAE. Misuse or abuse will be collected and reported in the safety database irrespective of it being associated with an AE/SAE within 24 hours of Investigator's awareness.

Table 10-1 Guidance for capturing the study treatment errors including misuse/abuse

Treatment error type	Document in Dosing CRF (Yes/No)	Document in AE eCRF	Complete SAE form
Unintentional study treatment error	Yes	Only if associated with an AE	Only if associated with an SAE
Misuse/Abuse	Yes	Yes	Yes, even if not associated with a SAE

For more information on AE and SAE definition and reporting requirements, please see the respective [Section 10.1.1](#), [Section 10.1.2](#) and [Section 10.1.3](#).

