12.5.2 Safety endpoints

For all safety analyses, the safety set will be used. All listings and tables will be presented by treatment group.

Safety summaries (tables, figures) include only data from the on-treatment period with the exception of baseline data which will also be summarized where appropriate (e.g. change from baseline summaries). In addition, a separate summary for death including on treatment and post treatment deaths will be provided. In particular, summary tables for adverse events (AEs) will summarize only on-treatment events, with a start date during the on-treatment period (treatment-emergent AEs).

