3. **Follow-up** (Day 16-29): After completion of the treatment period, patients will be observed until Day 29 or discharged from hospital, whichever is sooner. Study assessments to be conducted every 2 days for domiciled patients.
If patients are discharged from hospital prior to Day 29, a study visit conducted by telephone will occur on Day 29 (all other visits between discharge and Day 29 can be omitted).
4. **Safety follow-up visit assessment** (Day 45): A follow-up visit will be conducted at Day 45 if the patient is hospitalized. If patients are discharged from hospital prior to Day 45, a study visit will be conducted by telephone on Day 45.
5. **End of Study/Safety follow-up visit assessment** (Day 127): A follow-up visit for safety will be conducted at Day 127 if the patient is hospitalized. If patients are discharged from hospital prior to Day 127, a study visit will be conducted by telephone on Day 127.

2 First interpretable results (FIR)

Commercially Confidential Information

Commercially Confidential Information

3 Interim analyses

Commercially Confidential Information

4 Statistical methods: Analysis sets

For all analysis sets, participants will be analyzed according to the study treatment(s) randomized.

The Safety analysis set will include all randomized participants that have received any study drug.

Commercially Confidential Information

The PD analysis set will include all randomized participants with no protocol deviations with relevant impact on PD data.

The PD analysis set 2 will include all randomized participants with no protocol deviations with relevant impact on PD data. The participants that did not meet all the eligibility criteria mentioned in study protocol section 5 will be excluded from this set programmatically. Exclude participants with APACHE II score less than 10 at baseline programmatically.

The analysis sets and protocol deviation codes are related as follows:

Table 4-1 Protocol deviation codes and analysis sets

Category Deviation code	Text description of deviation	Data exclusion
	Subjects are excluded from safety analysis in case of these PDs:	Exclude subject from safety analysis set
INCL02	Informed consent form not obtained	Yes

Commercially Confidential Information

Category Deviation code	Text description of deviation	Data exclusion
	Subjects are excluded from safety analysis in case of these PDs:	Exclude subject from safety analysis set
INCL02	Informed consent form not obtained	Yes

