6.1.3 Statistical model, assumptions and hypotheses

The combined APACHE II endpoint as described in the estimand above is assumed to follow a normal distribution.

The primary endpoint will be analyzed by an analysis of covariance model including treatment group and the three stratification factors as factors and baseline APACHE-II score as a covariate. The analysis will be performed on the safety analysis set. The mean differences of MAS825 vs placebo will be reported with 90% confidence intervals (CIs). The 1-sided p-value for the overall treatment factor will be reported.

The primary objective will be achieved if the null hypothesis that MAS825 is not different to placebo is rejected using a one side alpha of 10%.

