6.3 Exploratory objectives

Commercially Confidential Information

Commercially Confidential Information

Commercially Confidential Information

7 Statistical methods for safety and tolerability data

All safety presentations and analyses will be based on the Safety Analysis Set.

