7.2.6 Adverse events

All information obtained on adverse events will be listed by treatment and subject.

Summary tables for adverse events (AEs) will summarize only on-treatment events, with a start date during the on-treatment period (treatment-emergent AEs).

The number and percentage of subjects with adverse events will be tabulated by body system and preferred term with a breakdown by treatment. Separate summaries will be provided for study medication related adverse events and other significant adverse events leading to discontinuation.

The number of deaths resulting from SAEs suspected to be related to study treatment and SAEs irrespective of study treatment relationship will be provided by SOC and PT until day 29 and after day 29.

The number of deaths resulting from SAEs suspected to be related to study treatment and SAEs irrespective of study treatment relationship will be provided by PT until day 29 and after day 29.

A subject with multiple adverse events within a body system is only counted once towards the total of this body system and treatment.

For the legal requirements of ClinicalTrials.gov and EudraCT, two tables are required:

on treatment emergent adverse events which are not serious adverse events and on treatment emergent serious adverse events and SAE suspected to be related to study treatment will be provided by system organ class and preferred term on the safety analysis set.

If for a same patient, several consecutive AEs (irrespective of study treatment causality, seriousness and severity) occurred with the same SOC and PT:

- a single occurrence will be counted if there is ≤ 1 day gap between the end date of the preceding AE and the start date of the consecutive AE
- more than one occurrence will be counted if there is > 1 day gap between the end date of the preceding AE and the start date of the consecutive AE.

For occurrence, the presence of at least one SAE / SAE suspected to be related to study treatment / non SAE has to be checked in a block e.g., among AE's in a ≤ 1 day gap block, if at least one SAE is occurring, then one occurrence is calculated for that SAE.

The SAEs and deaths by State will be graphically presented in a barchart. Refer to [Section 10.8](#) for details on the state.

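### Safety outputs are assigned to the randomised treatment, so a participant given the wrong infusion would be reported under a drug they did not receive

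*SAP*

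**What the plan says.** SAP section 4 and Protocol 12.1 carry the same assignment rule: "For all analysis sets, participants will be analyzed according to the study treatment(s) randomized". Both define the safety set by receipt: "The Safety analysis set will include all randomized participants that have received any study drug". Receipt of an infusion therefore decides who is in the set, and randomisation decides the arm in which they are shown.

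This set carries all safety output. SAP section 7 says "All safety presentations and analyses will be based on the Safety Analysis Set", and Protocol 12.5.2 says "For all safety analyses, the safety set will be used". SAP 7.2.6 adds: "The number and percentage of subjects with adverse events will be tabulated by body system and preferred term with a breakdown by treatment". It does not say that treatment there means the drug actually infused.

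The same set also carries the primary efficacy analysis. Of the APACHE II ANCOVA, SAP 6.1.3 says: "The analysis will be performed on the safety analysis set".

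On supply, Protocol 6.4 says: "Drug product will be supplied in bulk, so an unblinded pharmacist who is independent of the study team will be required". On errors, Protocol 10.1.5 says: "Study treatment errors and uses outside of what is foreseen in the protocol will be recorded on the appropriate CRF".

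**The concern.** An infusion reaction, an infection or a laboratory change follows from what was infused, not from what was allocated. Safety tables are normally attributed to treatment received for that reason. Here the plan states the opposite rule outright, so this is not a gap that a programmer could fill with the usual convention.

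Attribution matters more than usual in this trial. Protocol 8.4.7 says that the compound had not been used in a patient population before and that its safety profile was not established. The tables in SAP 7.2.6 also feed public registry reporting. For a rare serious event, one participant can decide whether the event appears under MAS825 at all.

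**Working it through.** **Reading the passages together**

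1. Assignment is by randomised treatment for all sets (SAP 4, Protocol 12.1).
2. Safety outputs use the safety set (SAP 7, Protocol 12.5.2).
3. Table 4-1 of the SAP, as far as it is visible, removes participants from the safety set only when informed consent was not obtained. A misdosed participant stays in, under the randomised arm.
4. No visible text gives an as-received rule, a rule for a wrong infusion, or an as-received sensitivity analysis. Parts of SAP 4 and Protocol 12.1 are redacted, but another set definition behind the redaction would not plainly undo a rule written for all sets.

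**The plan's own figure**

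The only design number needed is 60 per arm (Protocol 12.9.1). The stated 80% power reproduces from a difference of 3.6, an SD of 9.2 and one-sided alpha of 10%: 3.6 / (9.2 × √(2/60)) = 2.143; 2.143 − 1.282 = 0.862; Φ(0.862) = 80.6%. This is context only. Nothing below changes power, alpha or sample size.

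**Effect of one misattributed participant with an event**

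Assume 60 dosed participants per randomised arm. Let p be the as-randomised event proportion in the arm the participant leaves on reassignment, and q that in the arm joined. Numerators and denominators both move:

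- arm left: x/60 − (x−1)/59 = (1−p)/59
- arm joined: (y+1)/61 − y/60 = (1−q)/61
- change in risk difference: (1−p)/59 + (1−q)/61

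The documents give no event rates, so the counts are assumptions chosen to show the range:

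| Arm left | Arm joined | (1−p)/59 | (1−q)/61 | Change, points |
|---|---|---|---|---|
| 1/60 | 0/60 | 1.67 | 1.64 | 3.3 |
| 12/60 | 6/60 | 1.36 | 1.48 | 2.8 |
| 30/60 | 30/60 | 0.85 | 0.82 | 1.7 |

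The first row is the ceiling, because p cannot be below 1/60 when the participant had the event.

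**Direction for a single case**

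- Randomised to placebo, given MAS825, has the event. As randomised: 12/60 − 7/60 = 8.3 points. As received: 13/61 − 6/59 = 11.1 points. The plan's table understates the difference by 2.8.
- Randomised to MAS825, given placebo, has the event. As randomised: 12/60 − 6/60 = 10.0 points. As received: 11/59 − 7/61 = 7.2 points. The plan's table overstates it by 2.8.

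**Average effect**

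If m participants in each arm receive the other infusion, the expected as-randomised risk difference is (1 − 2m/60) times the true one. That is 96.7%, 93.3% and 90.0% for m = 1, 2 and 3. At assumed rates of 20% and 10%, the true 10.0 points becomes 9.7, 9.3 and 9.0. At m = 0 the two approaches give identical tables.

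**The case against.** The strongest reply is that the trigger is hypothetical and controlled. Each participant has one infusion. The IRT tells the unblinded pharmacist the allocated arm, and unblinded monitors check accountability and allocation against pharmacy records (Protocol 6.4). This stands: no misdosing rate is given, and I would expect few cases or none.

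A second reply is that a misdosed participant could be traced. Treatment errors go on the CRF (Protocol 10.1.5, Table 10-1), protocol deviations are listed and summarised (SAP 7.2.1), and adverse events are listed by participant (Protocol 12.5.2.1, SAP 7.2.6). A reader might infer that the event would be lost; the documents do not support that. The summary tables would still show it under the wrong drug.

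A third is that one set serves both purposes. A reader might infer that the whole safety set should switch to treatment received. That would also switch the primary ANCOVA (SAP 6.1.3) and supportive APACHE II analyses 2 to 4 (SAP 6.1.10), against an estimand defined on randomised treatment (Protocol 2.1, SAP 6.1.1). This objection stands in full and decides how the fix must be worded.

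Finally, no visible text says that the dosing CRF names the product infused, and blinded site staff would not normally know it. The change is therefore cheap but not free.

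**Conclusion.** The point holds as a minor correction to a stated rule. Safety outputs follow randomised treatment, and if a wrong infusion occurred they would attribute that participant's data to a drug not received.

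The size is conditional. One participant with an event moves the risk difference by at most about 3.3 points, less as the event becomes commoner, and by nothing if no one is misdosed. Two stronger readings should be avoided. The 3.3 points (about 1.7 per arm) is a ceiling for events of near-zero frequency, not a fixed cost per error. And the rule does not always hide a signal: dilution toward no difference is the average effect, while a single case can inflate the difference.

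These figures rest on 60 dosed participants per arm and on assumed event counts. The primary analysis is unaffected and is correctly by randomised treatment.

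**What to change.** Add one sentence to Protocol 12.1 and SAP 4, attached to outputs and not to the set: safety outputs are summarised by treatment actually received, while the primary ANCOVA and all other efficacy and pharmacodynamic analyses, including those on the safety analysis set, are by randomised treatment. Name the CRP and ferritin models among the latter, since Protocol 12.5.2.4 places them under a safety heading, and say which side the body temperature models in SAP 7.2.3 fall on. Add a listing of any participant whose received and randomised treatments differ.

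Take treatment received from the dosing and treatment-error CRF records. Confirm it where needed against the unblinded pharmacist's source documents and serum MAS825 levels. Protocol 6.6.1 describes serum levels for participants treated with MAS825, so check whether samples from participants randomised to placebo are assayed before relying on them.

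The cost is one extra treatment variable in programming and a small reconciliation task. Set membership, power and alpha do not change.

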4.1 Baseline

The baseline value is defined as the last assessment performed prior to randomization.

4.2 Unscheduled visits

Data collected at unscheduled visits will not be used for analysis by visit, but will be used to replace missing values if a Last observation carried forward (LOCF) approach is applied (i.e. for the mortality scores APACHE II, SAPS II and SOFA as described below).

Commercially Confidential Information

Commercially Confidential Information

6 Statistical methods for Pharmacodynamic (PD) parameters

6.1 Primary objective

The primary aim of the study is to evaluate the effect of MAS825 compared with placebo on the APACHE II score. A decrease in the score is considered a favourable outcome.

6.1.1 Variable

The primary clinical question of interest is: What is the effect of MAS825 compared with placebo in SARS-CoV-2 infected patients with COVID-19 pneumonia and impaired respiratory function on APACHE-II severity of disease score taking into account early discharge from hospital or death but regardless of investigational treatment discontinuation?

The justification for the primary estimand is that it will capture the combined effect of investigational treatment in participants who remain in hospital for 14 days, the effect on early discharge within 14 days and the effect on death rate within 14 days, in a manner than reflects clinical practice. In this document the primary estimand will be referred to as the “**combined APACHE II score**”.

The primary estimand is described by the following attributes:

- **Population:** SARS-CoV-2 infected patients with COVID-19 pneumonia and impaired respiratory function.
- **Endpoint:** APACHE II severity of disease score on Day 15 or on day of discharge (whichever is earlier) with worst case imputation for death. Participants who die on Day 15 or earlier will be assigned the highest observed APACHE II score of any of the participants at any time during the trial. Note this imputation for death takes precedence over the APACHE II score on day of discharge.
- **Treatment of interest:** the randomized treatment (the investigational treatment MAS825 or placebo).
- **Handling of remaining intercurrent events:** Treatment discontinuation for any reason will be ignored and thus follow a treatment policy strategy i.e. participants who discontinue treatment will be treated in the same manner as those that continue the treatment as planned.
- **Summary measure:** The difference in variable means between treatments.

APACHE II scores are on a range between 0 and 71 points, however, in practice it is rare for any patient to accumulate more than 55 points. A decrease in the APACHE II score is considered a favorable outcome.

The APACHE II scores are derived from a number of different clinical endpoints according to the scoring table as outlined in (Knaus et al., 1985) and listed in the Appendix. The handling of missing data is described in [Section 6.1.7](#).

6.1.2 Descriptive analyses

To assess the impact of the replacement with score values at early discharge and the worst case imputation for death on the combined APACHE II score the following summary statistics will be provided:

- only for the participants with an early discharge (i.e. prior to day 15): if APACHE II score values at the early discharge visit and the actual Day 15 visit are available these will be summarized separately by visit (“early discharge”, “Day 15”).
- In addition the frequency of worst case imputation for deaths per treatment group will be provided.

Panels of individual spaghetti plots over time for APACHE II scores and their change from baseline will be provided by treatment group. The profiles of all participants in the respective treatment group will be included in these graphs as grey lines in the background and the respective individual participants profile will be plotted with darker color in the foreground. It will be indicated by a symbol when a patient was discharged or died (see data handling rules below in [Section 6.1.8](#)).

The sub-scores contributing to APACHE II scores derivation would be summarized.

6.1.3 Statistical model, assumptions and hypotheses

The combined APACHE II endpoint as described in the estimand above is assumed to follow a normal distribution.

The primary endpoint will be analyzed by an analysis of covariance model including treatment group and the three stratification factors as factors and baseline APACHE-II score as a covariate. The analysis will be performed on the safety analysis set. The mean differences of MAS825 vs placebo will be reported with 90% confidence intervals (CIs). The 1-sided p-value for the overall treatment factor will be reported.

The primary objective will be achieved if the null hypothesis that MAS825 is not different to placebo is rejected using a one side alpha of 10%.

6.1.4 Sensitivity analysis for primary objective

The combined APACHE II endpoint as described in the estimand above is assumed to follow a normal distribution.

The primary endpoint will be analyzed by an analysis of covariance model including treatment group and the three stratification factors as factors and baseline APACHE-II score as a covariate. The analysis will be performed on the PD analysis set 2. The mean differences of MAS825 vs placebo will be reported with 90% confidence intervals (CIs). The 1-sided p-value for the overall treatment factor will be reported.

